6.3.2 Pharmacodynamic Analysis Population

All patients who have received at least one dose of the study medication and who have pharmacodynamic data available will be included in pharmacodynamic analyses. For these analyses, patients will primarily be grouped according to the treatment actually received; unless otherwise specified in the statistical analysis plan.

6.3.3 Pharmacokinetic Analysis Population

The population methods used for modelling of plasma concentration data will be described separately.

6.3.4 Safety Analysis Population

All patients who have received at least one dose of the study medication will be included in the safety analysis population. For these analyses, patients will be grouped according to the treatment actually received.

6.4 SUMMARIES OF TREATMENT GROUP COMPARABILITY

Demographic and baseline characteristics such as age, race, gender, ESSPRI score, ESSDAI score, salivary flow rate, etc. will be summarized for all randomized patients by treatment group.

6.5 SAFETY ANALYSES

Safety analysis will be performed for all patients in the safety analysis population. All safety parameters will be listed by patient and summarized in tables. Safety will be determined by AEs, laboratory tests, vital signs, ECGs and physical examinations.

There will be no formal statistical analyses of safety data; data will be presented using appropriate summary statistics and graphical plots as appropriate.

Exposure to study medication will be summarized by total duration of study medication and cumulative dose using descriptive statistics. No statistical testing is planned for safety analyses. Dose modifications, interruptions and the reasons will be presented.

6.5.1 Adverse Events

The original terms recorded on the eCRF by the Investigator for adverse events will be standardized by the Sponsor.

AE data will be reported in listings and presented in frequency tables by MedDRA terms. AEs will be summarized by mapped term and appropriate thesaurus level. If applicable, summaries of AE by seriousness and relationship to study treatment will be presented, as well as summaries of AEs leading to death, premature withdrawal from study treatment.

6.5.2 Clinical Laboratory Test Results

All clinical laboratory data will be stored on the database in the units in which they were reported. Patients' listings and summary statistics at each assessment time will be presented using the International System of Units (SI units; *Système International d'Unités*). Laboratory data not reported in SI units will be converted to SI units before processing.

Laboratory test values will be presented by individual listings with flagging of values outside the normal ranges. Summary tables of change from baseline over time based on SI (Standard International) units will be displayed. Shifts in grade from baseline to the worst grade observed during treatment will be presented for selected laboratory parameters.

6.5.2.1 Standard Reference Ranges and Transformation of Data

Roche standard reference ranges, rather than the reference ranges of the central lab/Investigator, as applicable, will be used. For most parameters, the measured laboratory test result will be assessed directly using the Roche standard reference range. Certain laboratory parameters will be transformed to Roche's standard reference ranges.

A transformation will be performed on certain laboratory tests that lack sufficiently common procedures and have a wide range of Investigator ranges (if applicable), e.g., enzyme tests that include AST, ALT, and alkaline phosphatase and total bilirubin. Since the standard reference ranges for these parameters have a lower limit of zero, only the upper limits of the ranges will be used in transforming the data.

6.5.2.2 Definition of Laboratory Abnormalities

For all laboratory parameters included, there exists a Roche predefined standard reference range. Laboratory values falling outside this standard reference range will be labeled "H" for high or "L" for low in patient listings of laboratory data.

In addition to the standard reference range, a marked reference range has been predefined by Roche for each laboratory parameter. The marked reference range is broader than the standard reference range. Values falling outside the marked reference range that also represent a defined change from baseline will be considered marked laboratory abnormalities (i.e., potentially clinically relevant). If a baseline value is not available for a patient, the midpoint of the standard reference range will be used as the patient's baseline value for the purposes of determining marked laboratory abnormalities. Marked laboratory abnormalities will be labeled in the patient listings as "HH" for very high or "LL" for very low.

6.5.3 Vital Signs

Vital signs data will be presented by individual listings with flagging of values outside the normal ranges and flagging of marked abnormalities. In addition, tabular summaries will be used, as appropriate.

6.5.4 ECG Data Analysis

ECG data will be presented by individual listings with flagging of values outside the normal ranges and flagging of marked abnormalities. In addition, the 12-lead triplicates will be averaged out. All analyses of QT data will be based on averages of the triplicate

measures at each scheduled time-point. These averages will be derived prior to any further data manipulation. Tabular summaries will be used, as appropriate.

6.5.5 Concomitant Medications

The original terms recorded on the patient's eCRF by the Investigator for concomitant medications will be standardized by the Sponsor by assigning preferred terms.

Concomitant medications will be presented in summary tables and listings. The dose and/or frequency of use of selected medications commonly prescribed to patients with Sjögren's syndrome will also be summarized.

6.6 EFFICACY ANALYSES

6.6.1 Primary Efficacy Endpoint

The primary endpoint is the proportion of patients who have ≥ 3 point reduction from baseline in ESSDAI score after 12 weeks of treatment. The proportion of *patients* who have ≥ 3 point reduction from baseline in ESSDAI score after 12 weeks of treatment will be compared between the two treatment arms using a Pearson Chi-square test (*two sided p-values, alpha 0.05*). The difference in proportions and corresponding 95% confidence interval (CI) will be provided. *Patients with missing data at Week 12 will be treated as non-responders in the analysis.*

Sensitivity analyses will be conducted if deemed necessary, including sensitivity analyses for handling missing data (e.g., *completer's analysis* or *last observation carried forward (LOCF) method* for missing observations).

In addition; the proportion of patient who have ≥ 3 point reduction from baseline in ESSDAI score after 12 weeks of treatment will be analyzed using a logistic regression model, adjusting for baseline ESSDAI score.

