4.3 METHOD OF TREATMENT ASSIGNMENT AND BLINDING

4.3.1 Treatment Assignment

Subjects will be randomly assigned to RO5459072 or placebo treatment groups in a 1:1 ratio using interactive voice/web-based response system IxRS (IvRS and IwRS).

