4.6.1.3 Disease-Specific Assessments

4.6.1.3.1 ESSDAI

EULAR Sjögren's Syndrome Disease Activity Index (ESSDAI) will be employed to assess disease activity at baseline and during the treatment phase. The ESSDAI is a physician-assessed disease activity index for primary Sjögren's syndrome developed by the EULAR consortium ([Seror et al 2010](#); [Seror et al 2015](#)). It consists of 44 items in 12 organ-specific 'domains' contributing to disease activity (constitutional, lymphadenopathy, articular, muscular, cutaneous, glandular, pulmonary, renal, peripheral nervous system [PNS], central nervous system [CNS], hematological, biological). Each domain is assessed for activity level (i.e., no, low, moderate, high) and assigned a numerical score based on pre-determined weighting of each individual domain. An overall score is then calculated as the sum of all individual weighted domain scores.

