6. STATISTICAL CONSIDERATIONS AND ANALYSIS PLAN

The database will be cleaned and frozen when all patients have completed the study or discontinued. The treatment assignment will then be unblinded and analyses will be performed on all data.

All efficacy outcomes will be analyzed using modified intent-to-treat population (mITT) which is defined as all randomized subjects who received any study medication and have evaluable measurement of the parameter of interest at baseline and at least one post-baseline visit. For all efficacy analyses, the treatment groups will be based on the treatment assigned at randomization.

All safety analyses will include all randomized patients who have received any study drug. For these analyses, patients will be grouped according to the treatment actually received.

There will be no adjustment made for any multiple comparisons. To aid the interpretation from the formal hypothesis testing, two-sided 95% confidence intervals will be provided.

Descriptive summaries will include mean, standard deviation, median and range for continuous variables and counts and percentages for categorical variables.

Details of statistical analyses will be provided in the statistical analysis plan.

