6.3 ANALYSIS POPULATIONS

6.3.1 Efficacy Analysis Population

All efficacy outcomes will be analyzed according to the mITT principle. The mITT population will comprise of all patients who are randomized, received study drug and have evaluable measurement of the parameter of interest at baseline and at least one post-baseline visit. For all efficacy analyses, the treatment groups will be based on the treatment assigned at randomization.

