6.6.2 Secondary Efficacy Endpoints

Secondary endpoints that are binary will be analyzed using similar methods used for analyzing the primary endpoint.

Continuous secondary endpoints will be analyzed using a Mixed Model for Repeated Measures (MMRM) approach incorporating all observed data up to 12 weeks of treatment. The MMRM will include the absolute change from baseline as the dependent variable. The fixed effects in the model will include treatment, visit (week), treatment-by-visit (weeks) interaction, along with baseline score as continuous covariates. An unstructured variance-covariance structure will be applied to model the within-patient errors, and the restricted maximum likelihood method will be used for estimating the variance components. The denominator degrees of freedom will be estimated using *the Kenward-Roger approximation*.

The least squares mean of change from baseline for each treatment group together with a 95% CI will be calculated from the MMRM model for each visit. At Week 12, the placebo-corrected difference will be estimated from the same MMRM model and will be used to test the null hypothesis of zero difference.

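### The deciding responder test ignores baseline ESSDAI, while the baseline-adjusted model already planned for the same endpoint is only an additional analysis

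*Combined protocol and SAP*

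**What the plan says.** Section 6.6.1 compares the proportions with a drop of at least 3 ESSDAI points at Week 12: they "will be compared between the two treatment arms using a Pearson Chi-square test" ("two sided p-values, alpha 0.05"). The difference in proportions is reported with a 95% CI, and patients with missing Week 12 data count as non-responders. The synopsis says the same. Section 6.6.1 then adds that the same proportion "will be analyzed using a logistic regression model, adjusting for baseline ESSDAI score", without saying which effect measure that model will report.

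Four other places bear on this:

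- Section 6.6.2 already adjusts the continuous endpoints, including ESSDAI change, for baseline: the MMRM has its fixed effects "along with baseline score as continuous covariates".
- Section 6.3.1 admits to the mITT population only patients who "have evaluable measurement of the parameter of interest at baseline and at least one post-baseline visit".
- Section 4.3.1 says "Subjects will be randomly assigned to RO5459072 or placebo treatment groups in a 1:1 ratio" and names no stratification factor.
- Section 4.6.1.3.1 describes the ESSDAI: "An overall score is then calculated as the sum of all individual weighted domain scores".

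**The concern.** Response is a fixed absolute drop on a weighted sum, so the chance of responding probably depends on the starting score. Nothing in the randomisation balances that score between arms. Every patient in the mITT analysis has a baseline value, so adjusting for it excludes nobody.

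Section 6.1 gives power of 58% to 80% with 35 per arm and says that practical considerations set the sample size. If baseline is at least moderately prognostic, the plan rests its primary inference on the less powerful of two tests it intends to run. The crude difference is unbiased over repeated trials. In a trial with a visible baseline imbalance, however, it is shifted, and the analysis that removes the shift is not the primary one. No baseline-adjusted difference in proportions is specified in Section 6.6.1.

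**Working it through.** **Inputs from Section 6.1:** n = 35 per arm, placebo rate 25%, differences of 25 and 33 points, two-sided alpha 0.05. **Assumed:** the strength of the baseline association, which the documents do not give. It is shown as a range that includes none.

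**1. The plan's own power.** Power = Φ{[d − 1.96·√(2p̄(1−p̄)/n)] / √[(p0(1−p0) + p1(1−p1))/n]}.

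- 25% vs 50%: p̄ = 0.375. (0.25 − 1.96 × 0.1157)/0.1118 = 0.207, so power is 58.2%.
- 25% vs 58%: p̄ = 0.415. (0.33 − 1.96 × 0.1178)/0.1110 = 0.893, so power is 81.4%.

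Exact binomial enumeration gives 58.9% and 80.8%. The stated 58% to 80% is reproduced.

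**2. Validity of the planned test.** The exact type I error of the chi-square at 35 per arm is 5.3%, 4.8% and 5.2% at common rates of 15%, 25% and 35%. It holds its level.

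**3. Effect of adjustment.** There were 20,000 simulated trials per scenario, with normal and skewed baselines. Monte Carlo error is about 0.35 points for power. Changes are in percentage points and were taken before rounding.

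| Baseline OR per SD (assumed) | Chi-square, 25% vs 50% | Logistic Wald (change) | Standardised difference, corrected SE (change) | Wald change, 25% vs 58% | Chi-square and Wald disagree at 0.05, 25% vs 50% |
|---|---|---|---|---|---|
| 1.0 | 59% | 58% (−1) | 58% (−1) | 0 | 4% |
| 1.5 | 59% | 59% (+1) | 60% (+1) | +1 to +2 | 6% |
| 2.0 | 59% | 62% (+3) | 62% (+4) | +3 | 10% |
| 2.5 | 59% | 64% (+5) | 65% (+6) | +5 to +6 | 13% |

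Chi-square power at 25% vs 58% is 80% to 81%.

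A rough check uses an effective n of 35/(1 − R²), where R² is the share of outcome variance explained by baseline. At R² = 0.05, n is 36.8 and power is 60.5% and 83.4% for the two differences, a gain of 2.3 and 2.0 points over step 1. At R² = 0.15, n is 41.2 and power is 65.4% and 87.4%, a gain of 7.2 and 6.0. The check ignores the cost of fitting the covariate.

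**4. Type I error of the candidates.** Common rate of 25% (all four ORs) and 40% (OR 1.0 and 2.0); Monte Carlo error about 0.0015.

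- Chi-square: 0.046 to 0.052.
- Logistic Wald: 0.042 to 0.050.
- Standardised difference, variance × N/(N−3), t on 67 df: 0.048 to 0.055.
- Standardised difference, uncorrected HC0 variance, normal reference: 0.057 to 0.064.

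A separate simulation of the likelihood-ratio test (6,000 trials per setting, ORs from 1.00 to 4.48) gave 0.056 to 0.062. The choice of Wald therefore matters.

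**5. Coverage of the 95% CI at 25% vs 50%** (6,000 trials): corrected standardised difference 94.4% to 95.0%, uncorrected 93.3% to 94.0%, crude difference 93.4% to 94.3%. Non-convergence of the logistic model was at most about 1 in 10,000.

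**6. Chance imbalance.** The SE of the baseline mean difference is √(2/35) = 0.239 SD. The chance of an imbalance above 0.3 SD in either direction is 2[1 − Φ(0.3/0.239)] = 21%. At 0.3 SD the crude difference shifts by about 2.5, 4 and 5 points for ORs of 1.5, 2.0 and 2.5. Its SE is √[(0.1875 + 0.25)/35] = 11 points, so the shift is under half an SE. The adjusted difference shifts by at most 0.2 points.

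**The case against.** The strongest reply is that nothing is wrong. The chi-square is valid, it matches the test used for sample size, and it needs no model. The adjusted model is prespecified in the same section, so only the order of two analyses is in dispute. All of that is true. It limits how serious the point is, but gives no reason for the less efficient test to be primary.

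The benefit is also assumed. At ORs of 1.0 and 1.5 the change at 25% vs 50% is one point or less either way. Entry requires ESSDAI of at least 5, so a patient still at that level has room for a 3-point drop. Scoring dropouts as non-responders would dilute an association if dropout is unrelated to baseline, and the simulations contain no dropout. This stands, and is why a range is shown.

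Disagreement between the tests runs both ways. In one run at 25% vs 50%, significance by chi-square only and by Wald only occurred in 2.5% and 1.2% of trials at OR 1.0, 3.1% and 3.4% at OR 1.5, and 3.2% and 6.7% at OR 2.0. The 4% to 13% is therefore how often the choice of test matters, not the gain; the net gain is the power change.

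This is a Phase 2a study with no decision rule tied to p < 0.05, and both results will be reported. The imbalance shift is modest. The standardised difference needs a small-sample correction and its type I error still reaches 0.055, which is why the p-value should come from the Wald test. Section 6 leaves details to the statistical analysis plan, so the effect measure can be settled there.

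**Conclusion.** The concern holds as a missed gain in precision. The planned test and its power statement are correct. At 25% vs 50%, promoting the adjusted model costs about 1 point of power if baseline ESSDAI is unrelated to response, gains about 1 point at an odds ratio of 1.5 per SD, and gains about 3 to 5 points (Wald) at 2.0 to 2.5. It also nearly removes the conditional shift caused by baseline imbalance.

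These figures assume 35 analysed patients per arm, no dropout and a logistic association with baseline. The strength of that association is the one input the documents do not supply, so confidence in the size of the gain is medium. The change is worth making because the covariate is collected, the model is planned and the downside is small.

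**What to change.** Amend Section 6.6.1, the matching synopsis text and the statistical analysis plan before the point in Section 6 at which "The treatment assignment will then be unblinded and analyses will be performed on all data":

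- **Primary analysis:** logistic regression of Week 12 response on treatment and continuous baseline ESSDAI in the mITT population, with the p-value from the Wald test of the treatment term. State that missing Week 12 data count as non-response in this model too.
- **Effect estimate:** the standardised difference in proportions from that model. Take the 95% CI from a robust variance multiplied by N/(N−3), with a t reference on N−3 degrees of freedom (67 if all 70 patients are analysed). Do not use an uncorrected delta-method or HC0 standard error with a normal critical value. Say that the Wald p-value governs if it and the interval differ.
- **Supportive:** the Pearson chi-square and crude difference with its CI, also used as the fallback if the model does not converge.
- **Section 6.1:** note that the power figures are for the unadjusted test and approximate the adjusted one, with about 1 point lost at worst over the range examined.

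The cost is document wording and a few lines of code. No new data are needed and no patient is lost from the analysis.

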4.5.2 Prohibited Therapy

Use of concomitant therapies which systemically suppress the immune system are not permitted during the study. Prohibited therapies are:

- Corticosteroid therapy exceeding 7.5 mg prednisone equivalent per day (see [Appendix 3](#)).
- Anti-CD20 therapy (e.g., rituximab) or other B cell-depleting therapy within 6 months of screening.
- Immunosuppressant therapy (e.g., abatacept, azathioprine, ciclosporin, etanercept, tofacitinib). Low dose methotrexate treatment (oral doses \leq 20 mg weekly) is, however, permitted.
- Cyclophosphamide.

Pilocarpine or drugs with similar pharmacological action should not be used within 12 hours prior to an assessment visit.

Because RO5459072 is a substrate of CYP3A4 and P-gp, other prohibited medications are:

- Moderate or potent inhibitors of CYP3A4 (e.g., itraconazole, erythromycin, nefazodone).
- Strong inducers of CYP3A4 (e.g., rifampicin, carbamazepine).
- *Sensitive substrates of CYP3A4 with a narrow therapeutic index (e.g., alfentanil, colchicine, ethosuxamide, fentanyl, and pimozide).*
- Strong inhibitors of the transporter P-glycoprotein (P-gp) (e.g., quinidine, clarithromycin).

A full list of prohibited concomitant medications is provided in [Appendix 4](#).

RO5459072 weakly induces CYP3A4 activity in vitro. RO5459072 treatment therefore has the theoretical potential to cause a small decrease in exposure of concomitantly administered CYP3A4 substrates. For this reason, caution is advised when initiating study drug treatment in individuals already established on a stable dose of a CYP3A4 substrate, or starting dosing with a CYP3A4 substrate in individuals receiving study drug treatment. See Section [4.2.2](#) regarding use of hormonal contraception.

In vitro data indicate that RO5459072 weakly inhibits the transport of substrates of MDR1 (P-gp), OATP1B1 and MATE2-K transporters. The potential for RO5459072 to alter the pharmacokinetics of substrates of these transporters (e.g., digoxin, pravastatin, metformin, etc) in vivo cannot be entirely discounted. Therefore, caution is advised when

administering study drug treatment together with medications known to be substrates of these transporters.

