4.7 PATIENT, STUDY, AND SITE DISCONTINUATION

4.7.1 Patient Discontinuation

The Investigator has the right to discontinue a patient from RO5459072 or withdraw a patient from the study at any time. In addition, patients have the right to voluntarily discontinue study drug or withdraw from the study at any time for any reason. Reasons for discontinuation of study drug or withdrawal from the study may include, but are not limited to, the following:

- Patient withdrawal of consent at any time.
- Pregnancy.
- Any medical condition that the Investigator or Sponsor determines may jeopardize the patient's safety if he or she continues in the study.
- Investigator or Sponsor determines it is in the best interest of the patient.
- The patient requires corticosteroid therapy exceeding 7.5 mg prednisone equivalent per day, or the dose of existing corticosteroid therapy is increased during the study

treatment period (see Section 4.5.2 and Appendix 3), or institution of any other immunosuppressive therapy, or an increase in dose of existing therapy.

Every effort should be made to obtain information on patients who withdraw from the study. The primary reason for withdrawal from the study should be documented on the appropriate eCRF.

Patients will not be followed for any reason after consent has been withdrawn. Patients who withdraw from the study will not be replaced.

Under no circumstances will patients who enroll in this study and have completed treatment as specified, be permitted to be allocated a new randomization number and re-enroll in the study.

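### Only a missing Week 12 score counts as non-response, so a fall in ESSDAI observed after new or increased corticosteroid or immunosuppressive therapy can be counted as response to the assigned treatment

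*Combined protocol and SAP*

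**What the plan says.** - **Endpoint (Section 6.6.1).** Response is a fall in ESSDAI of 3 points or more at Week 12. On the comparison, the section reads: "point reduction from baseline in ESSDAI score after 12 weeks of treatment will be compared between the two treatment arms using a Pearson Chi-square". The definition sets no condition on other therapy or on staying on study drug.
- **Non-response rule (Section 6.6.1).** "Patients with missing data at Week 12 will be treated as non-responders in the analysis". No other event overrides an observed score.
- **Sensitivity analyses (Section 6.6.1).** "Sensitivity analyses will be conducted if deemed necessary, including sensitivity analyses". The examples given, a completers' analysis and LOCF, concern missing data.
- **Prohibition (Section 4.5.2).** "Use of concomitant therapies which systemically suppress the immune system are not permitted during the study".
- **Discontinuation (Section 4.7.1).** "Reasons for discontinuation of study drug or withdrawal from the study may include, but are not limited to, the following". One entry in that list begins: "The patient requires corticosteroid therapy exceeding 7.5 mg prednisone equivalent per day, or the dose of existing corticosteroid therapy is increased during the study". The same entry also names "institution of any other immunosuppressive therapy, or an increase in dose of existing therapy".
- **Analysis set (Section 6.3.1).** The mITT set needs randomization, study drug, a baseline value and one post-baseline value. Patients are analysed in the arm assigned. No per-protocol set is defined.
- **Use of the medication data.** Deviations are listed (Section 6.2). Concomitant medications are summarized and listed (Section 6.5.5). Neither is linked to responder status.
- **Secondary endpoints (Section 6.6.2).** Binary endpoints follow the primary method. The MMRM works by "incorporating all observed data up to 12 weeks of treatment", again with no rule for scores after such therapy.

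**The concern.** The protocol treats added immunosuppression as something that would obscure the effect of study drug: it prohibits it and requires stable doses of permitted background therapy. The primary analysis loses that protection once a Week 12 score exists. A patient who misses Week 12 is a failure. A patient who worsened, was given more immunosuppression, improved and was scored at Week 12 is a success for the assigned arm.

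If this happens more on placebo, the observed difference shrinks and a real effect may be missed. If it happens more on active, the trial may credit study drug with the effect of another treatment. With 35 patients per arm, very few such patients are needed to matter.

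**Working it through.** **Can the case arise under the text?** Three readings together show that it can.
1. Section 4.7.1 is permissive (*may include*), so the listed therapy does not compel any action.
2. It covers stopping study drug or leaving the study. A patient who only stops study drug can still attend Week 12.
3. Nothing in Sections 6.2, 6.3.1, 6.5.5 or 6.6.1 sets aside a score obtained after such therapy.

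**The plan's own power.** Section 6.1 gives 35 per arm, two-sided alpha 0.05, placebo rate at most 25%, difference 25 to 33 points, and power of at least 58% to 80%. With p̄ the mean of the two rates,

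power = Φ{ [ |p₂ − p₁| − 1.96·√(2p̄(1−p̄)/35) ] / √( [p₁(1−p₁) + p₂(1−p₂)]/35 ) }.

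- 25% v 50%: (0.25 − 0.2268)/0.1118 = 0.207, so power is 58.2%.
- 25% v 58%: power is 81.4%.

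Exact enumeration of the uncorrected Pearson test gives 58.9% and 80.8%. The stated range reproduces and is not in error.

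**Scenario with the same behaviour in both arms (assumed rates).** Take the planned rates as those obtained if such patients count as non-responders. Suppose 10% of placebo patients, all from the 75% who are non-responders, start such therapy: 10/75 = 13.3% of non-responders. Apply 13.3% to non-responders in both arms and let half of them reach a 3-point fall, so 6.67% of non-responders convert.

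- Placebo: 25 + 75 × 0.0667 = 30.0%.
- Active: 50 + 50 × 0.0667 = 53.3%, or 58 + 42 × 0.0667 = 60.8%.

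| Share of non-responders starting therapy | Placebo v active | Difference (points) | Power |
|---|---|---|---|
| None | 25.0% v 50.0% | 25.0 | 58.2% |
| 6.7% | 27.5% v 51.7% | 24.2 | 54.4% |
| 13.3% | 30.0% v 53.3% | 23.3 | 50.8% |
| None | 25.0% v 58.0% | 33.0 | 81.4% |
| 6.7% | 27.5% v 59.4% | 31.9 | 78.0% |
| 13.3% | 30.0% v 60.8% | 30.8 | 74.5% |

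The difference narrows here because placebo has more non-responders to convert.

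**Direction (assumed rates, as a share of all patients in the arm).**

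| Converted: placebo, active | From 25% v 50% | Power | From 25% v 58% | Power |
|---|---|---|---|---|
| 10%, 5% | 35% v 55% | 39% | 35% v 63% | 66% |
| 10%, 10% | 35% v 60% | 56% | 35% v 68% | 80% |
| 5%, 10% | 30% v 60% | 72% | 30% v 68% | 91% |

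With no true difference (25% in both arms), converting 10% of the active arm only raises the chance of a significant result from 4.8% to 15.0% by exact enumeration.

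**One patient.** 1/35 = 2.9 points. With z = |difference|/√(p̄(1−p̄)·2/35):
- 9/35 v 18/35: 0.2571/0.1164 = 2.21, p = 0.027. One more placebo responder, 10/35 v 18/35: 0.2286/0.1171 = 1.95, p = 0.051.
- 9/35 v 16/35: 0.2000/0.1145 = 1.75, p = 0.081. One more active responder, 9/35 v 17/35: p = 0.048.

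**The case against.** **Such patients may be few.** The therapy is not permitted, it is a named reason for discontinuation, treatment lasts 12 weeks, severe complications are excluded (Section 4.2.3), and background therapy must have been stable for at least 2 months. A patient who leaves without a Week 12 score is already a non-responder. This stands and limits the likely size, but it does not close the gap.

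**Analysing all observed scores as randomized is a recognised treatment-policy choice.** That is true, but the plan does not say it has made that choice. Scoring missing patients as failures points the other way, and a proof-of-concept trial is asking about the drug itself. The approach is better kept as a sensitivity analysis.

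**The rule may be in the statistical analysis plan.** Section 6 defers details there, and no separate text settling the point is in the document supplied. If a rule exists, Section 6.6.1 need only refer to it.

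A reader might also infer more than the documents support:
- *That the bias must run toward zero, or that power falls to 40% or 66%.* Those two powers follow from 30% v 50% and 30% v 58%, which let placebo non-responders convert but no active ones. Nothing in the documents supports that asymmetry.
- *That an early-termination score will stand in for Week 12.* Appendix 1 lists that visit in its own column, with no day assigned. The text does not say whether such a score within Day 84 ± 7 counts, so this is an ambiguity and not an established route.

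**Conclusion.** The gap is real on the text: a Week 12 score obtained after therapy that Section 4.5.2 does not permit can be counted as response. It should be closed, but its size is uncertain and probably modest. Under equal behaviour among non-responders in both arms, power falls by about 7 points (58% to 51%, or 81% to 74.5%), and by about 3 to 4 points at half that usage. These figures rest on assumed usage and improvement rates, on 35 analysed patients per arm, and on the planned response rates being those that hold when such patients count as non-responders.

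The direction is open: toward zero if placebo patients use more, a false-positive risk if active patients do, and little change if conversion is similar. The stronger reason to act is that one or two patients can move the primary p-value across 0.05, and without a written rule their classification could be argued after the results are known. The stated sample size and power are not in error.

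**What to change.** Before unblinding, add to Section 6.6.1 and the statistical analysis plan:

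1. For the analysis only, a patient who starts or increases corticosteroid or immunosuppressive therapy of the kind listed in Section 4.7.1 before the Week 12 ESSDAI is a non-responder, whether or not a Week 12 score exists. Define the qualifying medication entries so that the rule can be programmed without judgement.
2. The same rule applies to the ESSPRI responder endpoint.
3. An analysis of all observed Week 12 scores, regardless of such therapy, is a named sensitivity analysis.
4. State whether an early-termination ESSDAI within Day 84 ± 7 counts as Week 12.

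The responder rule does not settle the MMRM in Section 6.6.2; one further sentence should say whether scores after such therapy enter that model.

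The cost is a few sentences and a derivation from medication records that Section 4.5.1 already collects through follow-up. Patient care is unchanged. The downside is that response rates may be slightly lower, and a patient given such therapy for an unrelated illness also counts as a non-responder; the sensitivity analysis shows how much that matters.
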